**Inclusion criteria:**

- Male and female patients at least 18 years old
- Patients with confirmed pituitary origin of excess adrenocorticotrophic hormone (ACTH) production:
  - Persistent hypercortisolemia established by two consecutive 24 hr UFC levels at least 1.5x the upper limit of normal
  - Normal or elevated ACTH levels
  - Pituitary macroadenoma ( $>1$  cm) on MRI OR
  - Inferior Petrosal Sinus Sampling (IPSS) central to peripheral ACTH gradient  $>2$  at baseline and  $>3$  after CRH stimulation
  - Recurrent or persistent Cushing disease is defined as pathologically confirmed resected pituitary ACTH-secreting tumor, and 24 hour UFC above the upper limit of normal reference range beyond post-surgical week 6
  - Patients on medical treatment for Cushing's disease the following washout periods must be completed before screening assessments are performed :
    - Inhibitors of steroidogenesis (metyrapone, ketoconazole): 2 weeks
    - Somatostatin analogs (pasireotide): 2 weeks
    - Progesterone receptor antagonist (mifepristone): 2 weeks

- Dopamine agonists (cabergoline): 4 weeks
- CYP3A4 strong inducers or inhibitors: varies between drugs; minimum 5-6 times the half-life of drug

*Exclusion criteria:*

- Patients with compromised visual fields, and not stable for at least 6 months
- Patients with abutment or compression of the optic chiasm on MRI and normal visual fields
- Patients with Cushing's syndrome due to non-pituitary ACTH secretion
- Patients with hypercortisolism secondary to adrenal tumors or nodular (primary) bilateral adrenal hyperplasia
- Patients who have a known inherited syndrome as the cause for hormone over secretion (i.e. Carney Complex, McCune-Albright syndrome, MEN-1)
- Patients with a diagnosis of glucocorticoid-remedial aldosteronism (GRA)
- Patients with cyclic Cushing's syndrome defined by any measurement of UFC over the previous 1 months within normal range
- Patients with pseudo-Cushing's syndrome, i.e. non-autonomous hypercortisolism due to overactivation of the HPA axis in uncontrolled depression, anxiety, obsessive compulsive disorder, morbid obesity, alcoholism, and uncontrolled diabetes mellitus
- Patients who have undergone major surgery within 1 month prior to screening
- Patients with serum  $K^+ < 3.5$  while on replacement treatment
- Diabetic patients whose blood glucose is poorly controlled as evidenced by  $HbA1C > 8\%$

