## **Section 7.0 Assessment of Efficacy**

The primary efficacy population will include patients who had baseline mean UFC levels 1.5x above the upper normal range, and who completed the 4-cycle, 4-week treatment period with no more than 2 weeks of interrupted drug doses. Baseline UFC levels are defined as the mean of three 24-hour urine specimens collected within one week of baseline visit.

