### **Section 9.0 Statistics**

Due to the rarity of Cushing disease in the general population, it is difficult to do a randomized placebo controlled trial with sufficient sample size numbers to achieve adequate power. By using subjects as their own controls, we measure pre- and post-treatment changes on the same population, therefore alleviate the issues with recruitment.

We used a Simon exact single-stage phase II design (8) to determine the sample size for 80% power and a one-sided 0.05 significance level. The trial tests the null hypothesis that the seliciclib (response rate)  $\leq 5\%$  (unacceptable response rate) versus the alternative hypothesis that  $RR \geq 25\%$  (promising response rate). We enroll 16 patients. If at least 3 of the 16 respond, we conclude that seliciclib is promising in the treatment of ACTH-producing pituitary tumors.

A regression model will be used to investigate the relationship between end-of-study UFC and baseline UFC. The comparison between serum cortisol or plasma ACTH in patients who responded to seliciclib and in those who did not respond will be performed by a Student's *t* test. Categorical variables, i.e. normalization of 24 hour UFC, development of new pituitary deficits, and visual field deficits will be compared in the pre- and post- treatment time points using fisher's exact test.

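### Section 9.0 applies Fisher's exact test, a test for independent groups, to before/after data in the same patients; for two of its three variables the before count is zero by construction

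*Combined protocol and SAP*

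**What the plan says.** Section 9.0 (Statistics) justifies the single-arm design by within-patient comparison: "By using subjects as their own controls, we measure pre- and post-treatment changes on the same population". The sample size comes from an exact single-stage design with "80% power and a one-sided 0.05 significance level", an unacceptable response rate of 5% and a promising rate of 25%. Its decision rule reads: "If at least 3 of the 16 respond, we conclude that seliciclib is promising".

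The last sentence of the section covers three categorical variables: normalisation of 24-hour UFC, development of new pituitary deficits, and visual field deficits. It ends: "visual field deficits will be compared in the pre- and post- treatment time points using fisher's exact test". No paired test for categorical data is named anywhere.

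Two other places fix or nearly fix the before value for UFC. Section 7.0 limits the primary efficacy population to "patients who had baseline mean UFC levels 1.5x above the upper normal range". The inclusion criteria in Section 5.0 require "two consecutive 24 hr UFC levels at least 1.5x the upper limit of normal", and the exclusion criteria remove anyone with a normal UFC in the preceding month.

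**The concern.** There are two separate faults.

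**The before count is zero.** Nobody in the efficacy population can have a normalised UFC at baseline, because Section 7.0 requires a raised baseline mean. Among all enrolled patients this is nearly certain but not fixed, since screening and baseline UFC are separate collections. A new pituitary deficit cannot exist before treatment. For both variables the comparison is therefore 0/16 against k/16, and its p-value is a function of k alone.

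**The pairing is lost.** For visual fields a before/after comparison is a sensible question, because only unstable visual field compromise is excluded and a stable deficit may be present at entry. Fisher's test still treats the two readings on one patient as readings on two unrelated patients.

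What is at stake is reporting, not the go/no-go decision. UFC normalisation is the primary endpoint, so the plan prescribes two analyses of it with different null hypotheses: a response rate of at most 5%, and equal proportions before and after. The second carries no decision but can be non-significant when the first is met. For visual fields, the p-value reported for a safety variable would be wrong.

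**Working it through.** **Inputs from the documents.** n = 16, threshold r = 3, p0 = 0.05, p1 = 0.25, one-sided alpha 0.05, power 80% (Section 9.0); before count 0 for UFC (Section 7.0). The plan does not say whether Fisher's test is one- or two-sided, so both are shown. All 16 patients are taken as evaluable.

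**Step 1: reproduce the design.** With X binomial(16, p):
- Alpha = P(X ≥ 3 | 0.05) = 1 − (0.4401 + 0.3706 + 0.1463) = 0.043.
- Power = P(X ≥ 3 | 0.25) = 1 − (0.0100 + 0.0535 + 0.1336) = 0.803.

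Both agree with the stated 0.05 and 80%.

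**Step 2: UFC normalisation, 0/16 before against k/16 after.** With a zero before count the one-sided Fisher p is C(16,k)/C(32,k), and the two-sided p is twice that because the groups are equal. For k = 3: 560/4960 = 0.113, doubled 0.226. For k = 4: 1820/35960 = 0.0506, doubled 0.101.

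| Responders | Exact binomial against 5%, one-sided | Fisher one-sided | Fisher two-sided |
|---|---|---|---|
| 3/16 | 0.043 | 0.113 | 0.226 |
| 4/16 | 0.007 | 0.051 | 0.101 |
| 5/16 | 0.0009 | 0.022 | 0.043 |

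Fisher's test first falls below 0.05 at 5 responders on either sidedness.

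**Step 3: how often the two would sit awkwardly together.** At a true rate of 25%, P(X = 3) + P(X = 4) = 0.2079 + 0.2252 = 0.433. As a share of results that meet the rule: 0.433/0.803 = 54%.

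**Step 4: visual fields.** The documents give no expected rate, so these counts are assumptions: 16 patients, none resolved, a baseline deficits (0 to 4) that all persist, and b new deficits. Fisher compares a/16 with (a + b)/16. Exact McNemar uses only the patients who changed, so its two-sided p is 2 × 0.5^b (at most 1) whatever the baseline.

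| New deficits | Exact McNemar | Fisher, baseline 0/16 | 1/16 | 2/16 | 4/16 |
|---|---|---|---|---|---|
| 1 | 1.0 | 1.0 | 1.0 | 1.0 | 1.0 |
| 2 | 0.50 | 0.48 | 0.60 | 0.65 | 0.70 |
| 3 | 0.25 | 0.23 | 0.33 | 0.39 | 0.46 |
| 5 | 0.0625 | 0.043 | 0.083 | 0.113 | 0.149 |
| 6 | 0.031 | 0.018 | 0.037 | 0.054 | 0.073 |

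From a zero baseline, and with more than one new deficit, Fisher gives too small a p-value. With stable deficits at baseline it gives too large a one. It cannot be defended as conservative.

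**Step 5: the interval that matches the rule.** Exact (Clopper–Pearson) limits for 3/16 = 18.8%:
- 90% two-sided: 5.3% to 41.7%, which excludes 5%.
- 95% two-sided: 4.0% to 45.6%, which does not.

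The lower limit of the 90% interval corresponds to the one-sided 0.05 test.

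**The case against.** The strongest reply is that little depends on this test. The trial is an exploratory proof of concept, the decision rests on the responder count, and Sections 5.0 and 8.0 act on visual field worsening patient by patient. All of that stands, and it limits the severity. It does not make the test valid.

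The visual field counts at which the two tests fall on opposite sides of 0.05 are also unlikely here. Five or six new deficits would have to appear within 4 weeks in patients selected to exclude unstable fields and chiasm involvement with normal fields. At 1 to 3 new deficits neither test is near significance and the conclusion is the same. This is fair, and it is why the table includes the low counts.

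The 54% depends partly on sidedness. At 4/16 the one-sided Fisher p is 0.0506, barely over the line. Counting only 3/16 as clearly discordant, the share is 0.2079/0.803 = 26%. A non-significant Fisher result also does not contradict the rule, since it tests a different null hypothesis; the harm is confusion.

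Finally, the sentence can be read so that the word new governs visual field deficits too. Visual fields would then also start from zero and would call for an incidence instead of McNemar. Fisher's test is wrong on either reading.

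**Conclusion.** The concern holds. As written, Section 9.0 applies a test for independent groups to paired data, and for two of the three variables the before value carries no information. The sample size, type I error, power and 3-of-16 rule are unaffected.

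The practical effect is a redundant p-value of 0.113 or 0.226 beside a favourable result at 3/16, and 0.051 or 0.101 at 4/16. For visual fields, the p-value can be wrong in either direction. The UFC figures assume that all 16 patients are in the efficacy population; the visual field figures rest on assumed counts. It should be fixed before analysis, but it does not threaten the trial's main conclusion.

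**What to change.** Replace the last sentence of Section 9.0 with three statements:

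- **UFC normalisation.** Drop the before/after test and do not substitute McNemar, which would also depend on k alone. Report the responder proportion with the exact binomial test against 5% and an exact 90% two-sided confidence interval, which agrees with the one-sided 0.05 rule. If a 95% interval is preferred for presentation, say that it can include 5% at 3/16.
- **Visual field deficits.** Use the exact McNemar test on deficit present or absent, and show the numbers of new and resolved deficits. If only new deficits are meant, say so and report them as in the next item.
- **New pituitary deficits.** Report the incidence with an exact confidence interval among patients without the deficit at baseline, and state whether this is counted per hormone axis or per patient.

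The cost is a rewrite of one sentence. No new data are needed, and neither enrolment nor the decision rule changes.

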### **Section 10.0 Quality Control and Quality Assurance**

Only samples and data collected with appropriate consent will be used for the proposed analysis. Specimens and data collected under the proof of concept clinical trial of seliciclib will be coded in such a way so that other members of the research team will be unable to ascertain the identity of specific patients. All of our data will be maintained confidentially. Data will be kept in locked file cabinets and in password protected files on computer systems.

### **Section 11.0 Ethical considerations relating to the trial**

Subjects will be recruited from Cedars-Sinai Pituitary Center. They will be patients followed clinically. Patients will be approached regarding participation in the study and given consent forms to review at home. They will be reassured that their clinical care will not be affected if they choose not to participate. Patients will be given opportunities to ask questions and review the consent process. Once they consent and enroll in the study, their data will be de-identified for the duration of the study. All patients entering the trial will be given the study drug. There is no placebo arm. The risks of the study are related to the side effects of the study drug and patients will be monitored for this and informed on the effects. The benefits of the study are normalization of urinary free cortisol. There are potential conflicts of interest between the patient's need for surgical referral and participation in the research study. However, by limiting the study period to 4 weeks, which is the average pre-op preparation time for our pituitary surgery patients, we will minimize the conflict of interest.

### **Section 12.0 Data Handling and Recordkeeping**

Data will be maintained in separate research charts in a locked cabinet in a locked office. The data will be entered as well into an electronic database on a password-protected computer. Only study staff and the investigators will have access to these records.

### **Section 13.0 Financing and Insurance**

Funding for this study will be through a Cedars-Sinai institutional grant. Patients will only be charged for the initial MRI and visual field test.

### **Section 14.0 Publication Policy**

We intend to submit our research findings to relevant peer-reviewed journals for publication. We will submit data for presentation at international meetings. We will adhere to the NIH Grants

Policy Statement on Sharing of Biomedical Research Resources, including the "Principles and Guidelines for Recipients of NIH Research Grants and Contracts on Obtaining and Disseminating Biomedical Research Resources: Final Notice" (64FR 72090, December 23, 1999; and described at <http://ott.od.nih.gov/NewPages/RTguide/final.html>.

